4. ANALYSIS SETS AND HANDLING OF DEVIATIONS

The populations for analyses were defined as three analysis groups:

Data Sets	Definition Usage
All Randomized	Demographic Information is evaluated for those participants who participated in the bioequivalence study (i.e., all participants who were randomized). However, the participants who were replaced by the stand-by participants before the first administration of Study Interventions will be excluded from the analysis.
Safety	Safety is evaluated for those participants who were administered at least one dose of the Study Interventions.
PK	Pharmacokinetics is evaluated for those participants whose pharmacokinetics evaluation is possible by the completion of all planned pharmacokinetics blood collection schedules according to the Protocol, who do not exhibit concentrations exceeding 5% of the maximum plasma concentration (C_{max}) of the drug in the pharmacokinetics sample of prior to dosing and who have valid primary endpoints for both treatments. In the case of drop-outs, they are excluded from statistical analysis.

5. PHARMACOKINETIC AND SAFETY VARIABLES

5.1 PHARMACOKINETIC ENDPOINTS

Blood collection for pharmacokinetic analysis follows the schedule given in the BE Study Protocol. Pharmacokinetic parameters are calculated from the blood concentration-time data of 'metformin' using a non-compartmental method.

Parameter	Definition	Measuring method
AUC_{last}	Area under the plasma concentration versus time data pairs, where last is the time of the last quantifiable concentration	Linear trapezoidal method
AUC_{inf}	Area under the plasma concentration versus time data pairs, with extrapolation to infinity	$AUC_{last} + C_{last} / K_{el}$
C_{max}	Maximum plasma concentration	Directly observed from the analysis data.
T_{max}	Time to maximum plasma concentration	First observed time at which the maximum concentration is observed. Directly observed from the analysis data.
$t_{1/2}$	Elimination half-life	The apparent terminal half-life, calculated according to the equation $t_{1/2} = \ln(2) / K_{el}$ Where K_{el} is the elimination rate constant K_{el} from the linear regression analysis on the log-linear plot of the portion corresponding to the terminal phase of the blood concentration-time curve.
AUC_{last} / AUC_{inf}	The ratio of AUC_{last} to AUC_{inf}	AUC_{last} / AUC_{inf}

Type	PK Parameters
Primary endpoints	AUC _{last} , C _{max}
Secondary endpoints	AUC _{inf} (if data allows to calculate), AUC _{last} /AUC _{inf} (if data allows to calculate), t _{1/2} (if data allows to calculate) and T _{max}

5.2 SAFETY ENDPOINTS

The safety profile of the Investigational Medicinal Product will be assessed through the recording, reporting and analysis of baseline medical conditions, adverse events (AEs), Physical examination, vital signs, 12-lead ECG, and Clinical laboratory tests, Blood Sugar Test(BST).

6. PRESENTATION AND EVALUATION OF PLASMA CONCENTRATION AND PHARMACOKINETIC VARIABLES

6.1 PRESENTATION OF PLASMA CONCENTRATIONS

List subject, dosing group and actual blood collection interval of the blood collection time. In addition, list blood concentrations by actual blood collection time, by dosing group and by time. And descriptive statistics for blood concentrations shall be presented.

The blood concentration-actual time curve of the drug for each subject and dosing group is presented. In addition, arithmetic and geometric mean and concentration graphs for each dosing group are presented.

If the concentration prior to administration is below the lower limit of quantification (BLQ), it is indicated as "0".

All other BLQ values are considered to be "blank" when calculating the geometric mean and "0" when calculating the arithmetic mean.

When calculating the pharmacokinetic parameters, the concentration of BLQ in the curve of the rising section is entered as "0" and the concentration of BLQ in the terminal phase is treated as "blank".

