4.1.2 Rationale for determination of Pharmacokinetics Time Points

Idkaidek et al (1) provided the following pharmacokinetic parameters of oral metformin 750 mg XR in healthy adults:

Formulation / Pharmacokinetic parameter	XR-Fasted	XR-Fed
C_{max} (ng/mL)	832 (300)	794 (143)
T_{max} (h)	4.3 (1.0)	6.35 (1.1)
$t_{1/2}$ (h)	3.8 (1.2)	3.66 (0.8)

Metformin mean (SD) plasma pharmacokinetic parameters after 750 mg XR (Extended Release) oral doses to healthy volunteers

In the Article 15 (2) of the Korean guideline "Standard on Pharmaceutical Equivalence Study"¹², it is mentioned that "Blood collection shall be conducted with sufficient time period of more than 3 times the elimination half-life or AUC_{0-t} to reach at least 80% of AUC_{∞} .". It is recommended that blood sampling needs more than 12 times and more than twice blood collection before reaching to the highest blood concentration (C_{max})."

To reflect this requirements, the blood collection time period shall be 32 hours which is more than 3 times the elimination half-life, and totally 16 blood samples will be collected as in below.

1) Part 1 (Fasted state)

- Number of samples: 16 times (once just before administration of study intervention, 15 times thereafter)
- Sampling time: Before administration (just prior to administration) of study

intervention and 0.5, 1, 2, 2.5, 3, 3.5, 4, 5, 6, 7, 8, 10, 12, 24 and 32 hours thereafter
2) Part 2 (Fed state)

- Number of samples: 16 times (once just before administration of study intervention, 15 times thereafter)
- Sampling time: Before administration (just prior to administration) of study intervention and 1, 2, 3, 4, 5, 5.5, 6, 6.5, 7, 8, 9, 10, 12, 24 and 32 hours thereafter

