8.5 Pharmacokinetics

- The following PK parameters will be calculated, when appropriate:

Parameters will be calculated from the metformin blood concentrations.

Symbol	Definition	Measuring method

AUC _{last}	Area under the plasma concentration versus time data pairs, where _{last} is the time of the last quantifiable concentration	Linear trapezoidal method
AUC _{inf}	Area under the plasma concentration versus time data pairs, with extrapolation to infinity	AUC _{last} + C _{last} / K _{el}
C _{max}	Maximum plasma concentration	Directly observed from the analysis data
T _{max}	Time to maximum plasma concentration	First observed time at which the maximum concentration is observed, directly observed from
t _{1/2}	Elimination half-life	The apparent terminal half-life, calculated according to the equation $t_{1/2} = \ln(2) / K_{el}$ Where K _{el} is the elimination rate constant K _{el} from the linear regression analysis on the log-linear plot of the portion corresponding to the terminal phase of the blood concentration-time curve
AUC _{last} / AUC _{inf}	The ratio of AUC _{last} to AUC _{inf}	AUC _{last} /AUC _{inf}

- The actual date and time (24-hour clock time) of each sample will be recorded to calculate actual time elapsed since the prior dose administration.

Blood sample amount and aliquots per time points of pharmacokinetics are as follows.

Part 1: Fasted state

Collection time (h)	0	0.5	1	2	2.5	3	3.5	4	5	6	7	8	10	12	24	32
Sample amount (mL)	5	5	5	5	5	5	5	5	5	5	5	5	5	5	5	5
Aliquots	2	2	2	2	2	2	2	2	2	2	2	2	2	2	2	2

Part 2: Fed state

Collection time (h)	0	1	2	3	4	5	5.5	6	6.5	7	8	9	10	12	24	32
Sample amount (mL)	5	5	5	5	5	5	5	5	5	5	5	5	5	5	5	5
Aliquots	2	2	2	2	2	2	2	2	2	2	2	2	2	2	2	2

- The quantification of metformin in plasma will be performed using a validated analytical method (UPLC-MS/MS; LLOQ 20 ng/mL). Concentrations will be used to evaluate the PK of metformin.
- Remaining samples collected for analyses of metformin concentration may also be used to evaluate safety or efficacy aspects related to concerns arising during or after the study.
- Details on processes for collection and shipment of these samples are in the SOP of Clinical Facility. Retention time and possible analyses of samples after the end of study are specified in the respective ICF.

1) Blood Collection Method

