8. LIST OF STATISTICAL APPENDICES

The numbers assigned to tables, lists and graphs were assigned during the analysis stage, and the final number will be assigned when the result report is generated. TLF is provided separately fasted and fed.

List of Tables

Table 1	Summary of Disposition
Table 2.1	Adverse events after dosing
Table 2.2	Adverse events after dosing related to the study drug
Table 2.3	Adverse events after dosing not related to the study drug
Table 2.4	Non-serious TEAEs by SOC and PT at a Frequency Threshold of 5%
Table 3	Concomitant Medication
Table 4	Summary Statistics of demographic characteristics
Table 5	Summary Statistics of Vital signs
Table 6.1	Summary Statistics of Laboratory tests
Table 6.2	Summary of Clinical significance of Laboratory tests
Table 7.1	Summary Statistics of 12-lead ECGs

List of Tables

Table 7.2 Summary of Clinical significance of 12-lead ECGs

Table 8 Summary of Clinical significance of Physical examination

Table 9 Summary Statistics of Blood Sugar Test(BST)

Table 10 Summary of Parametric statistical analysis of plasma metformin pharmacokinetic variables

Table 11 Summary of Non-parametric statistical analysis of plasma metformin pharmacokinetic variable

List of Figures

Figure 1 Plasma metformin arithmetic and geometric mean concentrations

Figure 2 Combined individual plasma metformin concentrations

Figure 3 Individual plasma metformin concentrations

Listings

Listing 1 Randomization and dosing

Listing 2 Demography and Anthropometry

Listing 3 Medical History

Listing 4 Physical examination

Listing 5 Vital Signs

Listing 6 Full blood count for subjects with abnormal values

Listing 7 Clinical chemistry for subjects with abnormal values

Listing 8 Urinalysis for subjects with abnormal values by Investigators Assessment

Listing 9 Pregnancy Test

Listing 10 Electrocardiography

Listing 11 Dosing

Listing 12 Prior/Concomitant medication

Listing 13 Adverse Events

Listing 14 Disposition

Listing 15 Blood sampling times and deviations

Listing 16 Blood Sugar Test(BST)

Listing 17 Plasma metformin concentrations (summary results)

Listing 18 Plasma metformin pharmacokinetic variables (summary results)

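### Post-dose BLQ values are left out of the geometric mean but counted as 0 in the arithmetic mean, so the reported geometric mean concentration cannot fall below 20 ng/mL and is biased upward where BLQ is common

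*SAP*

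**What the plan says.** SAP 6.1 has three BLQ rules, and Protocol Section 9, item 4, repeats them.

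- Pre-dose: "If the concentration prior to administration is below the lower limit of quantification (BLQ), it is indicated as" 0.
- Post-dose, for summary statistics: "All other BLQ values are considered to be" blank for the geometric mean and 0 for the arithmetic mean.
- For deriving PK parameters: BLQ on the rising part of the curve is entered as 0, and "the concentration of BLQ in the terminal phase is treated as" blank.

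SAP 6.1 also requires that "arithmetic and geometric mean and concentration graphs for each dosing group are presented". SAP Section 8 lists Figure 1 as "Plasma metformin arithmetic and geometric mean concentrations". The assay is described in Protocol 8.5 as "UPLC-MS/MS; LLOQ 20 ng/mL". In both parts sampling ends at "10, 12, 24 and 32 hours thereafter" (Protocol 4.1.2). No text available to me sets a minimum quantifiable fraction for showing a mean.

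**The concern.** For one set of positive values, the geometric mean cannot exceed the arithmetic mean. Under this rule the two means come from different sets: the geometric mean from quantifiable participants only, the arithmetic mean from everyone, with the rest at zero. The first is pushed up and the second down.

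If many late samples are BLQ, the geometric mean curve levels off at or above 20 ng/mL while true concentrations go on falling. It then describes only the participants with the highest late concentrations, under a label that suggests the whole treatment group. At stake is the accuracy of the concentration tables and mean curves at the end of the profile.

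**Working it through.** The plan states no figure on this point, so there is none to reproduce.

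**Step 1: the floor.** Let p be the BLQ fraction at a time point, and let GM_q and AM_q be the means of the quantifiable values.

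- Reported geometric mean = GM_q, which is at least 20 ng/mL whatever the data.
- Reported arithmetic mean = (1 - p) x AM_q.
- The geometric mean exceeds the arithmetic mean exactly when p > 1 - GM_q/AM_q.

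If the quantifiable values are roughly log-normal, that threshold is 1 - 1/sqrt(1 + CV²): 4.2% at CV 30%, 10.6% at 50%, 18.1% at 70% and 29.3% at 100%. A hypothetical example with eight participants: values 60, 40, 30, 25 and 22 ng/mL plus three BLQ give an arithmetic mean of 177/8 = 22.1 and a geometric mean of 33.1.

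**Step 2: typical late concentrations.** Protocol 4.1.2 cites "pharmacokinetic parameters of oral metformin 750 mg XR in healthy adults", as mean (SD), fasted and fed: Cmax 832 (300) and 794 (143) ng/mL; Tmax 4.3 (1.0) and 6.35 (1.1) h; half-life 3.8 (1.2) and 3.66 (0.8) h. I scale Cmax by 500/750 and let it decline mono-exponentially from Tmax: C(t) = Cmax x (2/3) x 2^(-(t - Tmax)/half-life).

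- Fasted, 24 h: 554.7 x 2^(-19.7/3.8) = 15.3 ng/mL
- Fed, 24 h: 529.3 x 2^(-17.65/3.66) = 18.7 ng/mL
- Fasted, 32 h: 554.7 x 2^(-27.7/3.8) = 3.5 ng/mL
- Fed, 32 h: 529.3 x 2^(-25.65/3.66) = 4.1 ng/mL

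All four are below the LLOQ. The 3.27 h half-life used for the wash-out (Protocol 4.1.1) would put the 24 h values lower still: 554.7 x 2^(-19.7/3.27) = 8.5 fasted and 529.3 x 2^(-17.65/3.27) = 12.6 fed.

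**Step 3: simulation.** I drew 400,000 profiles per part, with independent log-normal Cmax and half-life and normal Tmax, using the cited means and SDs. They were grouped into trials of 38 (fasted) and 22 (fed), the evaluable numbers in Protocol 9.2.2. Means are in ng/mL. The last column is the share of trials, among those with any quantifiable value, in which the geometric mean exceeds the arithmetic mean.

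| Part, time | BLQ | Reported arithmetic | Reported geometric | Uncensored geometric | Geometric > arithmetic |
|---|---|---|---|---|---|
| Fasted 12 h | 1.2% | 133.2 | 114.1 | 111.3 | 0% |
| Fed 12 h | 0.0% | 181.5 | 169.7 | 169.7 | 0% |
| Fasted 24 h | 67.4% | 13.7 | 37.4 | 10.0 | about 100% |
| Fed 24 h | 58.3% | 14.6 | 32.6 | 15.7 | about 100% |
| Fasted 32 h | 93.2% | 2.3 | 31.3 | 2.0 | about 100% |
| Fed 32 h | 96.9% | 0.8 | 26.3 | 3.2 | about 100% |

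Check against Step 1, fasted 24 h: AM_q = 13.7/0.326 = 42.0, so the threshold is 1 - 37.4/42.0 = 11%, far below 67%. At 32 h, 6.6% of fasted trials and 50.5% of fed trials have no quantifiable value, and then no geometric mean exists.

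**Step 4: sensitivity to a longer terminal half-life.** Entries are the BLQ fraction, then the share of trials with geometric above arithmetic mean.

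| Half-life | Fasted 24 h | Fed 24 h | Fasted 32 h | Fed 32 h |
|---|---|---|---|---|
| x1.3 | 36.4%; 99.6% | 17.8%; 84.7% | 75.5%; about 100% | 76.0%; about 100% |
| x1.6 | 16.5%; 53.6% | 3.4%; 9.9% | 52.4%; about 100% | 41.7%; about 100% |
| x2 | 5.1%; 1.8% | 0.3%; 0.4% | 26.8%; 93.9% | 11.6%; 60.4% |

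**The case against.** The rule is pre-specified and identical in both documents. A geometric mean is not informative once a zero enters, so some special handling is unavoidable. This stands as an explanation of the rule, but it does not make the resulting late values describe the treatment group.

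The projection may also understate late concentrations. Protocol 2.2 describes slow release through a gel matrix, and mono-exponential decline from Tmax allows no absorption after the peak. This stands: the size at 24 h is conditional, as Step 4 shows. The 20 ng/mL floor needs no such assumption.

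Heavy BLQ would also show elsewhere: arithmetic means or medians near 0, the combined and individual curves (Figures 2 and 3) and the listed concentrations. SAP 7.1 includes N among the descriptive statistics, and the mock-ups it refers to are not in the public text, so I cannot say that a quantifiable count is absent from the tables. This limits the harm but does not correct the geometric mean.

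Three stronger readings are tempting and not supported:

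- A reader might infer that tail differences between Test and Reference are hidden. The arithmetic means and individual plots would still show them, and nothing in the documents predicts different BLQ fractions for the two formulations.
- A reader might take the mean curves to be the main display of the release profiles. Neither document gives them that status.
- A reader might infer from the title of Figure 1 that both means share one panel. The title does not settle the layout.

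**Conclusion.** The point holds as a minor, descriptive one. The floor at the LLOQ follows from the rule alone. On the protocol's cited values, about 58-67% of 24 h samples and 93-97% of 32 h samples would be BLQ. At 24 h the reported geometric mean would be about 33-37 ng/mL, where the uncensored value is 10-16 and the reported arithmetic mean about 14-15. These sizes rest on dose proportionality from 750 to 500 mg, mono-exponential decline after Tmax, and independent log-normal Cmax and half-life.

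It would be too strong to say that the geometric mean will exceed the arithmetic mean at every late time. That is likely at 32 h wherever a geometric mean exists, uncertain at 24 h once the half-life reaches about 1.6 times the cited value, and not expected at 12 h.

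The flattened mean curve feeds into no estimate. AUClast, Cmax and half-life come from individual profiles under the separate parameter rule, so the 90% confidence intervals and the bioequivalence conclusion are untouched.

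**What to change.** In SAP 6.1, add that a mean concentration, arithmetic or geometric, is tabulated and plotted only at time points where at least half of the participants on that treatment have a quantifiable value. Print the number quantifiable by treatment and time point in the concentration table.

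This governs where means are shown, not how they are calculated, so it can sit in the SAP alone. Protocol Section 9 can be aligned if the protocol is amended for other reasons; an amendment made only for this would need IRB/IEC approval (Protocol Appendix 2).

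The cost is one sentence and one table column. The downside is that some late means, mainly at 24 and 32 h, would be suppressed. The threshold also leaves some upward bias where fewer than half of the values are BLQ, which is why the count is needed as well.

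I would not substitute LLOQ/2 instead. At 32 h the geometric mean would become 10^0.932 x 31.3^0.068 = 10.8 fasted and 10^0.969 x 26.3^0.031 = 10.3 fed, against uncensored values of 2.0 and 3.2: a lower floor, but still a floor.

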6.2 DEVIATIONS, MISSING CONCENTRATIONS

When performing statistical analysis to derive summary tables and mean graphs, concentration values are calculated as missing if any of the following is met:

- If actual blood collection has not been performed (Not Applicable)
- If the sample is missing (Missing Data)

6.3 PHARMACOKINETIC PARAMETERS

Pharmacokinetic parameters are calculated from the pharmacokinetic evaluation analysis group who have completed all study procedures and shall be presented up to the three decimal places.

The actual blood collection time is used to calculate pharmacokinetic parameters and to present individual blood concentration-time patterns. If it is impossible to calculate the pharmacokinetic parameters using the subject's concentration data, it is indicated as NC (i.e. not calculated). When performing statistical analysis for summary tables, NC values are calculated as missing data.

If the value of the pharmacokinetic parameter is biased due to an unexpected event (e.g., vomiting before the administered drug is completely absorbed), it is indicated as a footnote in the summary table. It is not used for the statistical analysis.

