6.3.2 Blinding

Blinding Method

Not applicable, this is an open-label study.

Assignment Method Retention

Not applicable, this is an open-label study.

Unblinding Clinical Studies for Sample Analysis of Special Data

This is an open-label study. However, the Analytical Facility will initially be blinded to prevent biases that might affect the result of sample analysis. The randomized sample code will be unblinded to the Analytical Facility only following the completion of sample analysis. Analytical Facility initiates statistical analysis after receiving the unblinded sample code from the Clinical Facility.

The samples from Part 1 (Fasted state) and Part 2 (Fed state) that are delivered to the Analytical Facility are blinded so that Information on administration of study intervention (Test or Reference, blood collection time, Period) are not known. Samples are randomized according to the SOP of Clinical Facility to assign sample codes to the samples.

- The blinded sample code should be indicated only on the sample or source data (Eppendorf tube, Box, Sample transfer related documents, etc.). Example of Eppendorf tube label is as follows.

Protocol No. CCI	Part 1 or CCI
Sampling time point, period and Participant number / PPD	
For Analysis or Back-up / AN or BU	

Information on blinded sample is not disclosed to the Analytical Facility until the concentration measurement is completed. Once the concentration analysis at the Analytical Facility is completed, the concentration of each sample from Part 1 (Fasted state) and Part 2 (Fed state) is informed to the Clinical Facility. After the Principal Investigator of Clinical Facility receives the concentration of each sample from Part 1 (Fasted state) and Part 2 (Fed state) from the Analytical Facility, he/she provides the blinded information on the sampling time and period to the Analytical Facility. After the Analytical Facility confirms the blinded information on the sampling time and period, the Analytical Facility performs Incurred Sample Reanalysis (ISR). After the Principal Investigator of Clinical Facility receives the ISR result from the Analytical Facility, he/she provides the blinded information on the sample code. After the Analytical Facility confirms the blinded information on the sample code, the sample code is unblinded.

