7.1 Discontinuation of Study Intervention

If a clinically significant finding is identified (including changes from baseline in QT/QTc interval corrected using Bazett's formula [QTcB]) after enrollment, the Investigator or qualified designee will determine if the participant can continue in the study and if any change in participant management is needed. This review of the ECG printed at the time of collection must be documented. Any new clinically relevant finding should be reported as an AE.

The Section 1.3 ([Schedule of Activities](#)) specifies the data to collect at study intervention discontinuation and follow-up, and any additional evaluations that need to be completed.

7.1.1 **Temporary Discontinuation**

Not applicable.

7.1.2 **Rechallenge**

Not applicable.

7.2 **Participant Discontinuation/Withdrawal from the Study**

- A participant may withdraw from the study at any time, at his/her own request (i.e. withdrawal of consent), and without giving a reason.
- The participant may be withdrawn by the Investigator due to participation in another clinical study.
- The participant may be withdrawn at any time at the discretion of the Investigator for safety, behavioral, compliance, or administrative reasons.
- If Principal Investigator (or delegated investigators) decides that the study cannot be continued by occurrence of Adverse Events/ Adverse Drug Reaction/ Serious AE
- If the participant arbitrarily takes any medication that is expected to affect the evaluation of safety and pharmacokinetic characteristics of the study intervention
- If a serious violation of the protocol is found during the study that belongs to inclusion/exclusion criteria
- If the Sponsor, MFDS or IRB requests suspension of the study
- If protocol non-compliance is found during the study
- The SoA specifies the data to collect at study discontinuation and follow-up, and any additional evaluations that need to be completed
- The participant may be withdrawn if the participant has difficulties in collecting blood samples
- The participant may be withdrawn if the participant vomits or has diarrhea during PK sampling periods
- The participant will be withdrawn if the participant is pregnant

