9.3 Populations for Analyses

The analysis populations are specified below. The final decision to exclude participants from any analysis population will be made during a data review meeting prior to database lock.

Analysis Set	Description
All Randomized	Demographic Information is evaluated for those participants who participate in the bioequivalence study (i.e., all participants who were randomized). However, the participants who were replaced by the stand-by participants before the first administration of study interventions will be excluded from the analysis.

Analysis Set	Description
Safety	Safety is evaluated for those participants who were administered at least one dose of the study interventions.
PK	Pharmacokinetics is evaluated for those participants whose pharmacokinetics evaluation is possible by the completion of all planned pharmacokinetics blood collection schedules according to the Protocol, who do not exhibit concentrations exceeding 5% of the maximum plasma concentration (C_{max}) of the drug in the pharmacokinetics sample of prior to dosing and who have valid primary endpoints for both treatments.

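### SAP 6.3 drops a PK value from the bioequivalence test when it is judged biased by an event, with no time criterion, closed event list or blinding, so event-related exclusions can depend on the result

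*SAP*

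**What the plan says.** - **Trigger (SAP 6.3):** "If the value of the pharmacokinetic parameter is biased due to an unexpected event (e.g., vomiting before the administered drug is completely absorbed". The affected value is footnoted in the summary table.
- **Consequence (SAP 6.3):** "It is not used for the statistical analysis".
- **PK set (SAP 4; same condition in protocol 9.3):** limited to participants "who have valid primary endpoints for both treatments". The word valid is not defined.
- **Who decides and when (protocol 9.3):** "The final decision to exclude participants from any analysis population will be made during a data review meeting prior to database lock".
- **Withdrawal (protocol 7.2):** "The participant may be withdrawn if the participant vomits or has diarrhea during PK sampling periods". This is discretionary.
- **Blinding (protocol 6.3.2):** the trial is open-label. For the laboratory, "The randomized sample code will be unblinded to the Analytical Facility only following the completion of sample analysis". Once measurement is finished, "the concentration of each sample from Part 1 (Fasted state) and Part 2 (Fed state) is informed to the Clinical Facility". Then, "Analytical Facility initiates statistical analysis after receiving the unblinded sample code from the Clinical Facility".
- **Non-compliance (protocol Appendix 2):** significant protocol non-compliance also leads in principle to exclusion from the PK analysis, with an open list of reasons.

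**The concern.** An exclusion rule for a bioequivalence test should turn on a recorded fact settled without sight of the result. This one turns on whether the parameter value is biased and whether absorption was complete. Without a clock time, the natural way to answer either question is to look at the concentration profile.

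The word unexpected does not narrow the rule, because protocol 2.3 and 6.9 name vomiting and diarrhea as known effects. Vomiting is given only as an example, so other events could qualify.

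The decision affects the primary test directly. With participant within sequence as a fixed effect, losing one period's value removes that participant from the test-reference contrast. If two participants have the same event and only the one with a low test/reference ratio is dropped, the estimate moves towards equivalence and a product at the limit passes more often than the nominal 5%.

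**Working it through.** **1. Can the decision be made with the result in view?**

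- The site knows treatment throughout and learns every concentration once measurement ends, before the laboratory is unblinded (protocol 6.3.2).
- The review meeting has one stated condition, that it precedes database lock (protocol 9.3). Neither document says it is held without concentrations or treatment codes.
- Withdrawal under protocol 7.2 is a separate route. A withdrawal made while samples are being collected comes before any concentration exists. The gap concerns participants who had an event, stayed in, and are judged later under SAP 6.3.

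**2. Inputs** (protocol 9.2.2, 9.1)

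| | Part 1 (fasted) | Part 2 (fed) |
|---|---|---|
| Within-participant CV (Cmax) | 25% | 18.7% |
| Evaluable N | 38 | 22 |
| Drop-out | about 20% | about 35% |

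Assumed ratio 0.95, one-sided alpha 0.05, limits 0.80 to 1.25.

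**3. Reproducing the plan's sample sizes**

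s_w = √ln(1+CV²); SE = s_w·√(2/N); df = N−2; exact power of the two one-sided tests.

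- Part 1: s_w = 0.2462, SE = 0.2462·√(2/38) = 0.0565, power 90.9% at N=38 (89.4% at 36). 38/0.80 = 47.5, so 48.
- Part 2: s_w = 0.1854, SE = 0.1854·√(2/22) = 0.0559, power 90.6% at N=22 (87.8% at 20). 22/0.65 = 33.8, so 34.

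Both reproduce. With no selective exclusion, the exact type I error at a true ratio of 0.80 is 5.0% in each part.

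**4. Effect of selective exclusion**

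Each participant's log test-reference difference is drawn from a normal distribution with mean ln 0.80 and SD s_w·√2 (0.348 in Part 1, 0.262 in Part 2). A random share q has a qualifying event. The estimate is the average of the two sequence means, with the variance pooled within sequence and df equal to the number retained minus 2. Equivalence is declared if the 90% CI lies within the limits. There were 40,000 trials per setting, so the Monte Carlo standard error near 5% is √(0.05·0.95/40,000), about 0.11 percentage points. The documents give no single-dose event rate, so q is an assumption.

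| Exclusion, one endpoint in one part | Part 1, n=38 | Part 2, n=22 |
|---|---|---|
| All event-affected, blind to result (q = 5% to 20%) | 4.9% to 5.1% | 4.9% to 5.0% |
| Event-affected with below-average ratio, q = 5% | 6.4% | 5.9% |
| Same, q = 10% | 8.0% | 7.4% |
| Lowest ratio among event-affected only, q = 5% | 5.7% | 5.5% |
| Same, q = 10% | 6.7% | 6.2% |
| Single lowest ratio, event or not | 10.9% | 12.8% |

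Allowing for simulation error between runs, dropping the unfavourable event-affected participants gives about 5.2% to 8.2% across q = 2% to 10% and both parts. With no drop-outs (n=48 and 34), q = 10% gives 8.7% and 8.2%.

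**5. Hand check (q = 10%)**

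Dropping the lower half of the event-affected removes on average a fraction q/2 = 0.05 of participants, whose mean lies √(2/π) = 0.798 SDs below the centre. The retained mean shifts by 0.05·0.798·SD/0.95.

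- Part 1: 0.05·0.798·0.348/0.95 = 0.0146, so the ratio moves from 0.80 to 0.812 (simulated 0.811).
- Part 2: 0.05·0.798·0.262/0.95 = 0.0110, giving 0.809 (simulated 0.809).

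**The case against.** The strongest defence is that the rule is narrower than it looks and safeguards surround it.

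- **An event is required.** An odd profile with no event does not qualify. Participants stay in the clinic until 32 hours after each dose, and Appendix 5 asks for onset times where timing relative to dosing matters. A reader might infer that for an extended-release tablet complete absorption can be judged only from the concentrations. That goes too far: vomiting and its time can be recorded, and a rule could rest on them. What is missing is such a rule.
- **Dropped values are visible.** They are footnoted, and SAP 7.2 lists concentrations for the randomized group. The laboratory is blinded during measurement and exclusions come before lock. All of this stands and lowers the risk. Disclosure does not make the decision outcome-blind, though, and laboratory blinding protects the assay, not the exclusion decision.
- **Events may be rare.** A reader might take protocol 2.3 to mean that vomiting and diarrhea will affect more than one participant in ten. That figure covers five gastrointestinal symptoms in patients receiving metformin, and the same section expects fewer adverse events after single doses. The shares used here are therefore assumptions.
- **Worst-case figures exceed the rule.** Removing the single lowest ratio regardless of event gives about 11% to 13%, but SAP 6.3 does not permit that without an event. It is an upper bound for removing one participant, not an estimate.
- **All endpoints must pass.** SAP 3.1 requires AUC and Cmax to pass in both parts, so the overall false-positive rate cannot exceed the single-test figure. It can approach that figure if one endpoint in one part sits at the limit and the rest are clearly equivalent.

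**Conclusion.** The concern holds in limited form. SAP 6.3 lets a judgement about a parameter value decide entry to the primary test, and nothing in either document keeps that judgement from being made with concentrations and treatment known. At a true ratio of 0.80, for one endpoint in one part at the planned evaluable numbers, type I error is about 5% under outcome-blind exclusion. It is about 5.2% to 8.2% if only unfavourable event-affected participants are dropped.

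That range rests on assumed event shares of 2% to 10%, events unrelated to the ratio, and consistently adverse selection. It does not show that anyone selected, or would select, in this way. The inflation is modest, but the correction is cheap and removes the route, so the SAP should be changed.

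**What to change.** 1. In SAP 6.3, replace the value-based trigger with a list of qualifying recorded events and a time-after-dose criterion, set and justified by the sponsor in advance.
2. Reconcile that list with protocol 7.2 (vomiting or diarrhea during PK sampling), protocol 9.3 and the Appendix 2 non-compliance exclusions, so that all give the same analysis set. A rule confined to vomiting would not agree with them.
3. Decide and document the event-based exclusions before concentrations are released to the Clinical Facility. The full exclusion list cannot be closed then, because the pre-dose limit of 5% of Cmax and the need for calculable endpoints depend on concentrations. Apply those criteria afterwards by their fixed rules.
4. Report one sensitivity ANOVA that retains the excluded profiles whose parameters can be calculated.

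The cost is SAP wording, an earlier review of events and one extra model run. The downside is that an odd profile with no qualifying event stays in the analysis.
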